The data source will be Humana's Research Database (Louisville, KY), which contains claims data for all of Humana's fully-insured commercial and Medicare membership. The data for this study include member enrollment, medical, pharmacy and lab results data.

Study Design

The study will be a cluster randomized design of an educational intervention versus no intervention, stratified by value-based arrangement (value based or non-value-based). Eligible patients and providers, based on the inclusion and exclusion criteria, will be identified via administrative medical and pharmacy claims. Patients enrolled in Medicare Advantage Prescription Drug (MAPD) plans, excluding those who are dually eligible for Medicaid, in the

East region (Kentucky, Pennsylvania, West Virginia, 6 counties in south New Jersey) will be required to have an indication of T2DM and ASCVD (coronary artery disease, cerebrovascular disease, peripheral arterial disease of atherosclerotic origin) in addition to 12 months of pre-identification continuous enrollment. These patients must not be currently or recently been treated with one of the SGLT2i or GLP-1 RA medications.

A sample of patients and their attributed primary care providers from the identified eligible cohort will be identified. Primary care providers will be identified as a value-based care provider or a non-value-based care provider.

- Providers in non-value based arrangements include those in fee-for-service arrangements and those in the Star quality recognition program. Providers are automatically enrolled in the Star program if the practice has >30 Humana patients. As such, those providers aren't considered to be in a value-based arrangement since this program enrollment is by default.
- Providers in value-based arrangements include those in path-to-value or full value contracts.
 - Path-to-value arrangements are engaged in model practice, medical home, and/or shared savings arrangements. Practices in these arrangements typically have the opportunity to share in any monetary incentive by effectively managing costs and revenue, but are not at risk for owing a deficit as in a downside arrangement.
 - Practices in full value arrangements assume a certain proportion of risk for costs that exceed the premium (based on the proportion of risk assumed for Medicare Part A and B costs). However, the incentive opportunity is typically more substantial than that of practices in other programs.

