Among those primary care providers and patients eligible for the study, a simple, random sample of primary care providers will be selected to be included for the intervention and control groups. All eligible patients of the randomly selected providers will be included in the same treatment arm (i.e., no cross over of patients into intervention or control arms). Providers and their patients assigned to the intervention arm will be compared to the randomly assigned providers and patients who will not be receiving any educational outreach or messaging.

This study will utilize data from patients enrolled in a US Medicare Advantage plan, so the results may not be generalizable for younger patients in commercial plans or patients outside of the US. In addition, these data are from patients who have elected enrollment into one US plan (Humana), thus generalizability to other health plans or the US population of patients with T2DM and ASCVD may be limited. The inclusion/exclusion criteria are constructed to attempt to include the broadest sample of patients who could be eligible to receive this type of therapy.

Measures

Exposure

Intervention Group

Patients and providers receiving the educational outreach and messaging will be in the intervention group. There will be three rounds of outreach for patients and providers.

- Patients
 - Outreach 1: The first outreach will be a direct mailing to patients that will explain their CV risk, provide resources to understand their risk (e.g., ADA Know Diabetes By Heart), and encouraging discussion with their providers about strategies (including medical, pharmacological and lifestyle) to reduce their risk for future CV-related events.
 - Outreach 2: The second outreach will be a telephone call to patients that will reiterate the message in the letter that will take place approximately 3 weeks after the initial mailing was sent. Up to three call attempts will be made, with general messages being left asking for a return call if a voicemail is reached.
 - Outreach 3: The last outreach will be a direct mailing to patients reiterating the messages in the first two outreach attempts that will take place approximately 3 months after the initial mailing was sent.
- Providers

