 - Outreach 1: The first outreach to providers will be a fax or direct mailing to the primary care provider and specialist providers (endocrinologist or cardiologist). Fax will be the first and preferred method of communication. However, if the fax fails or if there is not a valid fax number on file, direct mail will be used. The communication will highlight the guideline-recommendations from the ADA and ACC regarding use of SGLT2i and/or GLP-1 RA medications for patients with T2DM and ASCVD. This mailing or fax to all applicable providers will also include the names and date of birth of the patients identified who may be eligible for this treatment. It will be noted in each communication that the primary care and specialist providers that have been identified as providing care for the patient will be sent the communication, as well, and the names of those providers will be furnished in the communication.
 - Outreach 2: The second outreach will be a telephone call to providers that will reiterate the message in the letter that will take place approximately 3 weeks after the initial mailing/fax was sent. While it will be requested to speak directly with the provider, nurses or other office staff may receive the call. Up to three call attempts will be made, with general messages being left asking for a return call if a voicemail is reached.
 - Outreach 3: Three months after the initial outreach, another mailed/faxed communication will be sent to the providers reiterating the messaging from the first two communications, and including the list of patients who are still eligible for treatment and also noting those who have received treatment.

Control Group

This will include the patients meeting the inclusion/exclusion criteria and their providers who were randomized to not receive the educational outreach and messaging.

Primary Outcome Measure:

1. Guideline-based SGLT2i or GLP-1 RA medication initiation (excluding combination products)
[Time Frame: 6-months] Proportion of patients who have ≥ 1 pharmacy claim for SGLT2i or GLP-1 RA medications with cardiovascular benefit (excluding combination products)

Secondary Outcome Measures:

1. Guideline-based SGLT2i or GLP-1 RA medication initiation (excluding combination products)
[Time Frame: 12-months]: Proportion of patients who have ≥ 1 pharmacy claim for SGLT2i or GLP-1 RA medications with cardiovascular benefit (excluding combination products)

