The eligible patients and providers will be identified based on the inclusion/exclusion criteria. The attributed providers for each patient will be identified. For the primary care providers, the risk arrangement in which they are currently contracted, will be identified. Providers will be equally randomized via a simple random sample across (stratified) non-value based (e.g., fee-for service) or value-based (i.e., path-to-value and full value) arrangements between the intervention and control arms. All of the eligible patients for each identified primary care provider will be included in the same study cohort (i.e., either all control or all intervention).

Demographic, clinical and socioeconomic characteristics in the 12-month baseline period for patients and providers will be described (n (%), mean [standard deviation (SD)], median [interquartile range (IQR)], minimum, maximum). To ensure representativeness of the randomized sample, the sample will be compared to that of the sampling frame using standardized differences. The comparability between the intervention and control arms will also be assessed with standardized differences. Standardized differences will be assessed for each variable using the following example formulae¹¹:

Continuous variables:

$$d = \frac{\bar{X}_{group1} - \bar{X}_{group2+3}}{\sqrt{\frac{s^2_{group1} + s^2_{group2+3}}{2}}}$$

Binary variables:

$$d = \frac{\hat{p}_{group1} - \hat{p}_{group2+3}}{\sqrt{\frac{\hat{p}_{group1}(1 - \hat{p}_{group1}) + \hat{p}_{group2+3}(1 - \hat{p}_{group2+3})}{2}}}$$

where \bar{X} represents the mean of the covariate, s^2 represents the sample variance of \bar{X} , and \hat{p} represents the prevalence of that covariate. Variables with a standardized difference less than 0.1 will be considered balanced.

The primary analytic cohort for this aim will consist of the patients/providers randomized to the control arm and the patients/providers randomized to the intervention arm who received at least the first outreach (i.e., no returned mailings/faxes).

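### Eligible primary care providers left out of the random draw could serve as extra controls, and omitting them from the effect analysis gives up precision of unknown size

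*Combined protocol and SAP*

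**What the plan says.** Study Design describes the study cohort as a subset of those eligible: "A sample of patients and their attributed primary care providers from the identified eligible cohort will be identified". After the exclusion criteria, the same section says that "a simple, random sample of primary care providers will be selected to be included for the intervention and control groups". The eligibility rules, including valid contact details and the limits of 3 to 50 eligible patients per provider, come before this draw.

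The Statistical Analysis Plan, Primary Objective, gives the allocation: "Providers will be equally randomized via a simple random sample across (stratified) non-value based (e.g., fee-for service) or value-based" arrangements. It adds that "the sample will be compared to that of the sampling frame using standardized differences", so baseline data on the whole frame will be in hand.

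Measures, Exposure, says "Patients and providers receiving the educational outreach and messaging will be in the intervention group". The control group consists of eligible patients and "their providers who were randomized to not receive the educational outreach and messaging". The effect analysis uses these two groups only: "The primary analytic cohort for this aim will consist of the patients/providers randomized to the control arm and the patients/providers randomized to the intervention arm", with the intervention side further limited to those reached by the first mailing or fax. The model is a logit mixed model with a random provider effect and the stratification variable.

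Undrawn eligible PCPs enter no effect estimate. The document gives neither a reason for this nor their number.

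**The concern.** A random draw from an already eligible frame creates three groups within each stratum: intervention, control and undrawn. The third group is formed by the same chance mechanism as the second and, as far as the protocol shows, is managed in the same way. The outcome is a pharmacy claim in a database that already covers the plan's members, so observing it needs no recruitment, contact or visit.

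The hypothesis is a 2-point absolute difference in an outcome that is probably uncommon, with patients clustered within providers. The document states no sample size, power or intracluster correlation. Extra randomly formed controls would narrow the confidence interval for the primary contrast and would help the subgroup analysis by arrangement that is mentioned under Limitations, where each estimate rests on fewer providers.

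**Working it through.** **No figure to reproduce.** The plan gives no number of providers or patients, power, intracluster correlation, frame size or sampling fraction.

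**Inputs from the document.** Equal allocation within stratum, a hypothesised difference of +2 points, and 95% confidence intervals (read as two-sided alpha 0.05).

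**Assumptions.** 80% power under the 1:1 analysis. Control initiation between 3% and 10%: the Background puts use of these drugs below 10%, but that figure is use, not new initiation. A common fraction f drawn in each stratum. The same cluster-size mix and intracluster correlation in drawn and undrawn providers, which a random draw gives in expectation, so that the design effect cancels.

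**Formula.** Hold the intervention arm fixed and multiply the controls by k. With equal variance per arm, the variance ratio against 1:1 is (1 + 1/k)/2. If a fraction f of the frame is drawn and split equally, each arm holds f/2 of the frame. All non-intervention providers make up 1 − f/2, so k = (1 − f/2)/(f/2). Substituting gives a variance ratio of 1/(2 − f) and an SE ratio of 1/√(2 − f). Power is Φ(2.8016 × √(2 − f) − 1.96), where 2.8016 = 1.96 + 0.8416.

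| f | k | SE ratio | Power (80% at 1:1) |
|---|---|---|---|
| 1.0 | 1.00 | 1.00 | 80% |
| 0.9 | 1.22 | 0.95 | 84% |
| 0.75 | 1.67 | 0.89 | 88% |
| 0.5 | 3.00 | 0.82 | 93% |
| 0.25 | 7.00 | 0.76 | 96% |
| 0.1 | 19.00 | 0.73 | 97% |
| limit f → 0 | – | 0.71 | 98% |

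Example, f = 0.5: 1/√1.5 = 0.816, and Φ(2.8016 × 1.2247 − 1.96) = Φ(1.471) = 0.929.

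**Sensitivity to equal variance.** Take an assumed 5% against 7%, ignore clustering, and set k = 3. The binomial variances are 0.05 × 0.95 = 0.0475 and 0.07 × 0.93 = 0.0651.
- Risk difference: √[(0.0475/3 + 0.0651)/(0.0475 + 0.0651)] = √(0.0809/0.1126) = 0.85.
- Log odds ratio, the scale of the planned model: √[(1/(3 × 0.0475) + 1/0.0651)/(1/0.0475 + 1/0.0651)] = √(22.38/36.41) = 0.78.

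The equal-variance value of 0.82 lies between the two. In a two-proportion calculation with the variance pooled under the null, doubling the controls raises 80% power to about 90% at every assumed control rate from 3% to 10%.

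**Why the stratum term matters.** Assume a frame of 1,000 PCPs with equal patient numbers, 700 value-based and 300 not, initiation of 6% and 4%, and no intervention effect. Draw 100 from each stratum and split each equally.
- Intervention and control each: (50 × 6% + 50 × 4%)/100 = 5.0%.
- Undrawn: (600 × 6% + 200 × 4%)/800 = 5.5%.
- Control plus undrawn: (650 × 6% + 250 × 4%)/900 = 5.44%.

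A crude comparison would be off by 5.0 − 5.44 = −0.44 points. If the draw is proportional (140 and 60), every group is at 5.4% and the bias is zero. The planned model already contains the stratum term, which removes this bias.

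**The case against.** The strongest reply is that nothing here is wrong. A stratified, equally allocated comparison of randomised arms is valid, and the proposal only improves efficiency. That stands.

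The size of the gain also cannot be read from the document. The sampling wording and the frame comparison point to a subset, but the Statistical Analysis Plan also uses the term simple random sample for the allocation itself. If nearly every eligible PCP is drawn, little is gained, and at f = 1.0 nothing is. That stands too, and is why the low end of the table matters.

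A reader might infer that the control arm is too small or the trial underpowered. The document does not support this: with no sample size or power given, 1:1 precision may already be ample, and the 80% used above is an assumption.

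A reader might also infer that equal allocation should be abandoned, with intervention providers chosen up to outreach capacity and everyone else made control. No capacity or cost limit is stated. Without one, dividing the whole frame equally would be about as efficient as possible. Such a change would also redefine the allocation and the control group, which is more than this point needs.

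Finally, the explicit wording on receiving no outreach covers only providers randomised to control. That undrawn providers receive none follows from the definition of the intervention group, but it is an inference and needs confirmation.

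**Conclusion.** The point holds as one of lost efficiency. Undrawn eligible PCPs appear to be untreated, are exchangeable with controls within stratum, and can be observed in the same claims, yet they contribute only to the representativeness check. Under equal variance per arm, adding them reduces the standard error by anything from 0% (all drawn) to a limit of 29% (1 − 0.71), for example 5% at f = 0.9 and 18% at f = 0.5. The power figures rest on the assumed 80%.

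The conclusion depends on three conditions: the draw is a real subset taken at random after eligibility is fixed, undrawn providers get no study outreach during follow-up, and the stratum term stays in the model. Spill-over through shared specialists can reach undrawn providers' patients just as it can reach controls, so it does not separate the two groups.

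It would be wrong to infer that the planned comparison is biased because these providers are left out. Nor would adding them repair the limitation of the intervention arm to those reached by the first outreach: the interval around that selected contrast would narrow, and any bias in it would remain.

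**What to change.** Keep the stratified 1:1 draw. Before outcomes are seen, prespecify in the Statistical Analysis Plan an analysis that pools all undrawn eligible PCPs and their eligible patients with the control arm. Use the same August 2021 index date, the same outcome definition, and the same mixed model with the random provider effect and the stratum term. State whether it is primary or supporting.

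Confirm and record that undrawn providers and their patients receive no study outreach through the 12-month follow-up. Report the numbers of PCPs and patients eligible and drawn in each stratum, so that f is known and the reader can see how much the extra controls add.

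The cost is added plan text and a larger claims extract. Allocation in this analysis will be unequal and may differ by stratum, so the stratum term cannot be dropped.

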After the mailing (or fax) has been sent, a follow-up call to providers and patients will be conducted to ensure the message was received, reiterate the content of the initial outreach, and encourage discussions between patients and providers about CV risk reduction strategies. This call will be planned to take place within a few weeks (~3 weeks) from the initial mailing. While it will be requested to speak directly with the provider, nurses or other office staff may receive the call. Up to three call attempts will be made, with general messages being left asking for a return call if a voicemail is reached.

Three months after the initial outreach, another mailed/faxed communication will be sent to the providers reiterating the messaging from the first two communications, and including the list of patients who are still eligible for treatment and also noting those who have received treatment. The patients will also receive another direct mail communication approximately 3 months after the initial outreach reiterating the messaging from the first two communications.

The primary outcome for this study is the initiation of guideline-recommended SGLT2i or GLP-1 RA medications with CV benefit (excluding combination products) within 6-months of the initial outreach. Secondary outcomes include: 1) initiation of the medications of interest (excluding combination products) within 12 months of the initial outreach; 2) initiation of guideline-recommended SGLT2i or GLP-1 RA medications with CV benefit (including combination products) within 6-months of the initial outreach; 3) initiation of guideline-recommended SGLT2i or GLP-1 RA medications with CV benefit (including combination products) within 12-months of the initial outreach; and 4) adherence to SGLT2i or GLP-1 RA medications 6-months post-initiation; and 5) persistence to SGLT2i or GLP-1 RA medications 6-months post-initiation.

Identification and randomization: July 2021 (date on which data extraction begins)

Index event: date of first outreach to patients/providers (August 2021)

Second outreach (calls): start 3 weeks post-index

Third outreach (mailing/fax): starts 3 months post-index

[figure not shown]
Pre-identification and pre-index: 12-months continuous enrollment

Post-index: none

Follow-up: the primary outcome will be evaluated at 6-months and a secondary outcome will be utilization at 12 months post-index

Full data period: up to 2 years pre-index to 12-months post-index (July 2019 – August 2022)

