2. Adherence and persistence to guideline-based SGLT2i or GLP-1 RA medications [Time Frame: 6-months] Adherence and persistence to SGLT2i or GLP-1 RA medications with cardiovascular benefit (excluding combination products)

3. Guideline-based SGLT2i or GLP-1 RA medication initiation (including combination products)
[Time Frame: 6-months]: Proportion of patients who have ≥ 1 pharmacy claim for SGLT2i or GLP-1 RA medications with cardiovascular benefit (including combination products)

4. Guideline-based SGLT2i or GLP-1 RA medication initiation (including combination products)
[Time Frame: 12-months]: Proportion of patients who have ≥ 1 pharmacy claim for SGLT2i or GLP-1 RA medications with cardiovascular benefit (including combination products)

Baseline covariates:

- Demographics
 - Age
 - Sex
 - Race (as available; Black, White, other, unknown/missing)
 - Population density (e.g., rural, urban, suburban)
 - Chronic special needs plan enrollment (as available)
- Clinical characteristics
 - Elixhauser comorbidity index (based on medical claims)⁷⁻⁹
 - RxRisk V (comorbidity index based on medications as proxy)¹⁰
 - Prior MI, stroke, revascularizations
 - Number of unique medications
 - Use and type of antihyperglycemic medications (by class)
 - Use and type of cardiovascular medications (by class)
 - Indication of prior or current tobacco use
 - Indication of obesity and/or body mass index (BMI)

- Laboratory values (as available) (cholesterol, HbA1c, serum creatinine)
- All-cause healthcare resource utilization
 - Inpatient hospitalization
 - Total length of stay for hospitalizations
 - Emergency department visits
 - Provider encounters
 - Other outpatient visits (procedures, tests, imaging, durable medical equipment, other services, and unclassified)
- All-cause costs

Provider characteristics

- Value-based care arrangement for primary care providers
- Provider information (e.g., practice size, as available)

Statistical Analysis Plan

Primary Objective

Evaluate the impact of a dual educational outreach on 6-month frequency of SGLT2i and GLP-1 RA medication initiation by comparing patients and providers who receive and who do not receive the intervention.

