The adherence and persistence among those initiating SGLT2i and GLP-1 RA medications 6-months after the first medication fill will be described. Adherence to either class of medication will be measured as proportion of days covered [PDC] among those initiating treatment. The PDC will be the days' supply of medication divided by the number of days total in the follow-up. This will be described as a continuous measure (mean (SD), median (IQR), range) as well as categorically (e.g., $\geq 80\%$ and $< 80\%$ or other categorizations as appropriate). Persistence to the index medications will be defined as non-discontinuation of the treatment. A patient will be considered non-persistent if there is a > 90 day gap in therapy and persistent if there are no gaps in therapy or gaps in therapy of ≤ 90 days. Adherence and persistence may also be assessed at 12-months post-initiation based on results of 6-month measure.

Limitations

- Generalizability will be limited to the Humana MAPD population in the East region. However, the insights from this pilot may be used to inform and scale similar endeavors to other regions or populations.
- We cannot determine instances where a physician prescribed a treatment but the patient did not fill it (and why) or if a patient filled a prescription outside the data sources available to Humana (misclassification bias). Additionally, if patients do not stay enrolled in the health plan through the outcome observation period, then their outcomes may be misclassified as their data would not be available to capture. However, sensitivity analyses are planned to attempt to assess the impact of this bias.
- There may be barriers for providers to prescribe and/or patients to initiate and/or adhere to treatment, including factors related to increased member costs, not able to be ascertained from claims.
- Potential early adoption of an approved PQA measure linked with a risk arrangement in the region may impact outcomes. The study will randomize among patients and providers in different risk arrangements at the outset of the study and plan to conduct a subgroup analysis across arrangements.

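### The combination-product exclusion is carried into adherence and persistence, so later fills of a combination containing a listed drug are not counted as covered days

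*Combined protocol and SAP*

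**What the plan says.** The document describes these outcomes in three places.

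- **Study Design, list of secondary outcomes.** The two are named as "adherence to SGLT2i or GLP-1 RA medications 6-months post-initiation" and "persistence to SGLT2i or GLP-1 RA medications 6-months post-initiation". Neither mentions combination products, although each initiation outcome in the same paragraph states whether combinations are in or out.
- **Secondary Outcome Measures, item 2.** The exclusion appears here: "Adherence and persistence to SGLT2i or GLP-1 RA medications with cardiovascular benefit (excluding combination products").
- **Statistical Analysis Plan, Secondary Objectives.** The analysis is descriptive: "The adherence and persistence among those initiating SGLT2i and GLP-1 RA medications 6-months after the first medication fill will be described". For adherence, "Adherence to either class of medication will be measured as proportion of days covered [PDC] among those initiating treatment", and "The PDC will be the days' supply of medication divided by the number of days total in the follow-up". For persistence, "Persistence to the index medications will be defined as non-discontinuation of the treatment", with the rule that "A patient will be considered non-persistent if there is a > 90 day gap in therapy". This section does not mention combination products and has no rule for a change of product.

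The term index medications is not defined. Elsewhere in the document, index refers to the date of first outreach.

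**The concern.** For initiation, leaving out combination products decides which first fill makes a patient an initiator. That is a legitimate choice, and it matches the primary outcome. Applied to adherence and persistence, the same exclusion acts on later fills and does something different: it removes drug that the patient is actually receiving.

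The stated objective is adherence and persistence to SGLT2i and GLP-1 RA medications, that is, remaining on the therapy that the outreach promotes. A patient who moves without a break from a single-ingredient product to a combination containing a listed drug has remained on it. Under item 2 that patient loses PDC and, if the move is early enough, is recorded as having discontinued. The reported figures would then understate how long initiators stay on treatment. The plan also lets the 6-month results decide whether the measures are repeated at 12 months.

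**Working it through.** The documents give no expected value, sample size or power for adherence or persistence, so there is no figure to reproduce. The check applies the plan's own rules to one patient.

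**Inputs**
- PDC = days' supply / days of follow-up (Statistical Analysis Plan, Secondary Objectives).
- Non-persistent if a gap exceeds 90 days (same section).
- Adherence category cut at 80%, given there as an example.
- Window W of 6 months from first fill. The plan does not convert this to days; W = 180 is assumed, with 183 as an alternative.
- Combination fills not counted (Secondary Outcome Measures, item 2).

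**Patient.** Fully covered by a single-ingredient drug up to day s, then by a combination containing a listed drug, without a break, to the end of the window.

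**Formulas**
- Combination fills counted: PDC = W/W = 100%, gap = 0, persistent, for every s.
- Combination fills not counted: PDC = s/W and gap = W − s. Non-persistent if W − s > 90.

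**Results for W = 180, combination fills not counted**

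| Switch day s | PDC = s/180 | Gap = 180 − s | Persistence |
|---|---|---|---|
| 30 | 17% | 150 | non-persistent |
| 60 | 33% | 120 | non-persistent |
| 89 | 49% | 91 | non-persistent |
| 90 | 50% | 90 | persistent |
| 120 | 67% | 60 | persistent |
| 150 | 83% | 30 | persistent |

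**Thresholds**
- Persistence: 180 − s > 90 requires s ≤ 89. With W = 183, s ≤ 92.
- PDC below 80%: s < 0.8 × 180 = 144. With W = 183, 0.8 × 183 = 146.4, so a switch before day 147.
- If the optional 12-month assessment is run (365 days assumed): 365 − s > 90 requires s ≤ 274, so a larger part of the window is exposed.

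**Direction.** The PDC denominator is fixed, and leaving out fills can only reduce the numerator. Leaving out fills can also only lengthen gaps. Both measures can therefore only move down.

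**Size across the cohort.** If a fraction f of initiators switch in this way with first-drug cover ending by day 89, and would otherwise be persistent, the 6-month persistence proportion falls by f. The documents give nothing from which to estimate f.

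**The case against.** The strongest defence is that the exclusion keeps these outcomes on the same product set as the primary outcome, and that persistence to the products that define initiation is a coherent quantity. That is fair as a design position. It does not meet the stated objective, however, which concerns the drug classes, and the exclusion can still select the initiators without acting on their later fills.

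It is also fair that the consequence is limited. Both outcomes are secondary and described among initiators, no between-arm test is specified, and no initiation outcome is affected.

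A reader might infer more than the documents support, in four ways:

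- **That a move from one class to the other is scored as stopping, or makes a patient adherent and non-persistent at once.** Adherence is measured for either class, so such a move plausibly still counts in PDC. For persistence the reading depends on index medications, an undefined plural term. The sentence that uses it goes on to speak of the treatment, and the operative rule concerns a gap in therapy. It can equally mean the study's listed drugs in both classes, and on that reading a class switch without a break is persistent.
- **That any uncounted switch is recorded as discontinuation.** The 90-day rule prevents this for switches from day 90 onward in a 180-day window. Only PDC is affected there.
- **That the sections contradict one another.** The Study Design list and the Statistical Analysis Plan are silent on combinations for these outcomes; they do not say that combinations count. This is an omission, though two programmers working from different sections could produce different results.
- **That the bias amounts to a particular number of percentage points.** Without a switching rate, no such figure can be given.

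**Conclusion.** The point holds for combination products. Followed literally, item 2 removes covered days from patients who remain on a listed SGLT2i or GLP-1 RA in combination form. In the worked case of a switch at day 60, PDC is 60/180 = 33% instead of 100%, and the 120-day gap makes the patient non-persistent. This rests on a window of about 180 days and a switch without a break; using 183 days moves the thresholds by only three days.

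The bias runs downward only. Its overall size is unknown and could be negligible if few initiators switch. It touches two secondary descriptive measures and leaves the primary outcome alone. The undefined term index medications and the absence of a rule for moving between classes call for clarification; they are not shown errors. Overall this is an inexpensive improvement worth making before the measures are programmed.

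**What to change.** - In Secondary Outcome Measures, item 2, apply the combination-product exclusion to the qualifying first fill only. The set of initiators does not change.
- After that fill, count any fill of a product containing a listed SGLT2i or GLP-1 RA with CV benefit, single or combination, as covered days for both PDC and persistence.
- In the Statistical Analysis Plan, define index medications as the study's listed SGLT2i and GLP-1 RA medications, so that persistence matches the either-class scope of adherence.
- Use the same definition in the Study Design list, item 2 and the Statistical Analysis Plan, and state the length of the 6-month window in days.
- Report persistence to the first drug dispensed as a supporting description.

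The cost is a few sentences and some programming. The combination-product code list is already needed for secondary outcomes 3 and 4. The trade-off is that the main figure then describes staying on therapy and not staying on one product; the supporting description covers the latter.
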